#### **6.3.3. Pregnancy Tests**

A point-of-care urine pregnancy test will be performed at the Screening Visit (Day 0) and before each vaccine dose. At any time, a pregnancy test either via blood or point-of-care urine can be performed, at the discretion of the investigator. A by-subject listing will be provided for pregnancy tests.

#### **6.3.4. Vital Sign Measurements**

Vital sign measurements, including systolic and diastolic blood pressures, heart rate, respiratory rate, and body temperature, will be presented in a data listing. The values meeting the toxicity grading criteria (DHHS 2007) will be flagged in the data listing. The abnormalities meeting the toxicity grading criteria (Grade 2 or higher) in any vital sign measurement will be listed separately. If a subject has a vital sign result with Grade 2 or higher abnormality at any post injection visit, then all results of vital sign measurement for that subject will be presented in the listing.

Observed values and changes from baseline for all vital sign measurements will be summarized at each visit by vaccination group as defined in [Section 6.1](#). Shift from baseline in the toxicity grades at each visit and shift from baseline in the toxicity grades to the worst post-baseline result will also be summarized by vaccination group.

### **6.4. Immunogenicity Analysis**

The analyses of immunogenicity will be based on the PP Immunogenicity Subset and Immunogenicity Subset. The PP Immunogenicity Subset is the primary analysis population used in the immunogenicity analyses, unless otherwise specified. Subjects will be included in the treatment group to which they were randomized.

The GMT and geometric mean (GM) level will be calculated using the following formula:

$$10^{\left\{ \frac{\sum_{i=1}^n \log_{10}(t_i)}{n} \right\}}$$

where  $t_1, t_2, \dots, t_n$  are  $n$  observed immunogenicity titers or levels.

The geometric mean fold-rise (GMFR) measures the changes in immunogenicity titers or levels within subjects. The GMFR will be calculated using the following formula:

$$10^{\left\{ \frac{\sum_{i=1}^n \log_{10}\left(\frac{v_{ij}}{v_{ik}}\right)}{n} \right\}} = 10^{\left\{ \frac{\sum_{i=1}^n \log_{10}(v_{ij}) - \log_{10}(v_{ik})}{n} \right\}}$$

where, for  $n$  subjects,  $v_{ij}$  and  $v_{ik}$  are observed immunogenicity titers or levels for subject  $i$  at time points  $j$  and  $k$ ,  $j \neq k$

#### 6.4.1. Sampling of the Immunogenicity Subset

For the primary analysis of immunogenicity, and characterizing immunogenicity of the vaccine, a simple sampling method will be used for measuring bAb and nAb data from a sampled subset of trial participants.

##### Sampling Plan

The first 550 participants enrolled in Part 1A who meet all the criteria below will be selected.

- The participant is in Full Analysis Set.
- Baseline SARS-CoV-2 status is not missing.

In such case, approximately 362 participants who receive mRNA-1273 will be selected for the Immunogenicity Subset, with a target of 289 participants in the PP Immunogenicity Subset (adjusting for approximately 20% of participants who may be excluded from the PP Immunogenicity Subset, as they may have baseline positive SAR-CoV-2 status, or have no immunogenicity results due to any reason).

For the noninferiority tests of Ab GM and seroresponse rate at Day 57 in adolescents in Study P203 compared with that in young adults (18-25 years of age) from Study P301 receiving mRNA-1273, an immunogenicity subset of 340 young adults from Study P301

will be randomly selected from all participants (18-25 years of age) receiving mRNA-1273, with a target of 289 participants in the PP Immunogenicity Subset (using same definition as in Study P203) after adjusting for approximately 15% of participants not meeting inclusion criteria for PP Immunogenicity Subset.

#### **6.4.2. Immunogenicity Assessments**

There will be two types of immunogenicity assessments:

- Serum bAb by a multiplex serology assay specific to the SARS-CoV-2 S protein
- Serum nAb titer against SARS-CoV-2 as measured by pseudovirus and/or live virus neutralization assays

#### **6.4.3. Primary Analysis of Antibody-Mediated Immunogenicity Endpoints**

If an accepted serum Ab threshold of protection against COVID-19 is available based on data from other mRNA-1273 studies or external data, the number and percentage of participants with Ab greater than or equal to the threshold at Day 57 will be provided with a 2-sided 95% CI using the Clopper-Pearson method. If the lower bound of the 95% CI on the mRNA-1273 group is > 70%, the primary immunogenicity objective of this study will be considered to be met.

The percentage of participants with serum Ab greater than or equal to the threshold with 95% CI will be provided at each postbaseline time point. The CI will be calculated using the Clopper-Pearson method.

If an accepted serum Ab threshold of protection against COVID-19 is not established, the noninferiority of primary vaccine response as measured by Ab GM and seroresponse rate in adolescents compared with those in young adults (18-25 years of age) receiving mRNA-1273 will be assessed. The study is considered to meet the primary immunogenicity objective if the noninferiority of the immune response to mRNA-1273 as measured by both GM and seroresponse rate at Day 57 is demonstrated in adolescents in this study at a 2-sided alpha of 0.05, compared with those in young adults (18-25 years of age) in Study P301 receiving mRNA-1273.

An ANCOVA model will be carried out with Ab at Day 57 as a dependent variable and a group variable (adolescents in P203 and young adults in P301) as the fixed variable. The GM values of the adolescents at Day 57 will be estimated by the geometric least square mean (GLSM) from the model. The GMR (ratio of GM values) will be estimated by the ratio of GLSM from the model. A corresponding 2-sided 95% CI will be provided to assess the

difference in immune response for the adolescents in P203 compared to the young adults of 18-25 years of age in P301 at Day 57. The noninferiority of immune response to mRNA-1273 as measured by GM will be considered demonstrated if the lower bound of the 95% CI of the GMR is  $> 0.67$  based on the noninferiority margin of 1.5, and GMR point estimate  $> 0.8$  (minimum threshold).

The number and percentage (rate) of participants achieving Ab seroresponse at Day 57 will be summarized. The difference of seroresponse rates between adolescents receiving mRNA-1273 in P203 and young adults of 18-25 years of age receiving mRNA-1273 in P301 will be calculated with 95% CI. The noninferiority in seroresponse rate of adolescents in P203 compared to adults of 18-25 years of age in P301 will be considered demonstrated if the lower bound of the 95% of the seroresponse rate difference is  $> -10\%$  based on the noninferiority margin of 10%, and the seroresponse rate difference point estimate  $> -5\%$  (minimum threshold).

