#### 4.2. Statistical Hypothesis

- If an accepted serum Ab threshold of protection against COVID-19 is established for the primary immunogenicity objective, the null hypothesis is that the percentage of participants on mRNA-1273 with serum Ab equal to or above the established threshold at Day 57 is  $\leq 70\%$  (ie,  $H_0$ : percentage of participants on mRNA-1273  $\leq 70\%$  with serum Ab at Day 57 equal to or above the established threshold).

The study would be considered to meet the immunogenicity objective if the 95% confidence interval (CI) of percentage of participants on mRNA-1273 rules out 70% (lower bound of the 95% CI  $> 70\%$ ).

- If an accepted serum Ab threshold of protection against COVID-19 is not available for the primary immunogenicity objective, the immunogenicity analysis of primary vaccine response will be performed using the noninferiority tests of the 2 null hypotheses based on the 2 coprimary endpoints, respectively.

- Coprimary endpoint 1: Ab geometric mean (GM) value at Day 57

The null hypothesis:

$H^1_0$ : immunogenicity response to mRNA-1273 as measured by Ab GM value at Day 57 is inferior in adolescents (12 to < 18 years of age) receiving mRNA-1273 compared with that in young adults (18 to 25 years of age) receiving mRNA-1273 using Study P301 data.

The noninferiority in Ab GM in adolescents compared with that in young adults (18 to 25 years of age) is demonstrated by meeting both success criteria:

- The lower bound of the 95% CI of the geometric mean ratio (GMR) rules out 0.667 (lower bound > 0.667) using a noninferiority margin of 1.5.
- The GMR point estimate > 0.8 (minimum threshold).

The GMR is the ratio of the GM value of adolescents on mRNA-1273 in this study, Study P203, at Day 57 compared with the GM value of young adults (18-25 years of age) on mRNA-1273 in Study P301.

- Coprimary endpoint 2: Ab seroresponse rate at Day 57

The null hypothesis:

$H^2_0$ : immunogenicity response to mRNA-1273 as measured by seroresponse rate at Day 57 is inferior in adolescents (12 to < 18 years of age) receiving mRNA-1273 compared with that in adults (18 to 25 years of age) using mRNA-1273 Study P301 data

The noninferiority in seroresponse rate in adolescents compared with that in adults (18 to 25 years) is demonstrated by meeting both success criteria:

- The lower bound of the 95% CI of the seroresponse rate difference rules out -10% (i.e. lower bound > -10%) using the noninferiority margin of 10%.

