##### **Coprimary Endpoint 1: Ab geometric mean (GM) value at BD-Day 29**

The null hypothesis:

$H^1_0$ : immunogenicity response to mRNA-1273 BD as measured by Ab GM value at BD-Day 29 in adolescents (12-<18 years of age) in Study P203 Part 1C-1 is inferior compared with Ab GM value at Day 57 (28 days after Dose 2) in the primary series of mRNA-1273 in young adults (18 to 25 years of age) in Study P301.

The noninferiority in Ab GM value at BD-Day 29 in Study P203 Part 1C-1 compared with Ab GM value at Day 57 in the primary series in young adults (18 to 25 years of age) in Study P301 will be demonstrated by meeting both success criteria:

- The lower bound of the 95% CI of the geometric mean ratio (GMR) rules out 0.667 (lower bound > 0.667) using a noninferiority margin of 1.5.
- The GMR point estimate  $\geq 0.8$  (minimum threshold).

The GMR is defined as the ratio of GM value of Ab at BD-Day 29 in Study P203 Part 1C-1 compared with Ab GM value at Day 57 (28 days after Dose 2) following the primary series of mRNA-1273 in Study P301.

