##### **Coprimary Endpoint 2: Ab Seroresponse Rate (SRR) at BD-Day 29**

The null hypothesis:

$H^2_0$ : immunogenicity response to mRNA-1273 BD as measured by SRR at BD-Day 29 in adolescents (12-<18 years of age) in Study P203 Part 1C-1 is inferior compared with SRR

at Day 57 (28 days after Dose 2) following the primary series of mRNA-1273 in young adults (18 to 25 years of age) in Study P301.

- The noninferiority in SRR at BD-Day 29 compared with SRR at Day 57 (28 days after Dose 2) following the primary series of mRNA-1273 will be demonstrated by the lower bound of the 95% CI of the seroresponse rate difference  $\geq -10\%$  (i.e. lower bound  $> -10\%$ ) using the noninferiority margin of 10%.

The SRR difference is defined as the SRR at BD Day 29 in Study P203 Part 1C-1 minus the rate at Day 57 (28 days after Dose 2) following the primary series of mRNA-1273 in young adults in Study P301. The seroresponse is defined as Ab value change from baseline (pre Dose 1) below the LLOQ to  $\geq 4 \times \text{LLOQ}$ , or at least a 4-fold rise if baseline is  $\geq \text{LLOQ}$ .

The primary immunogenicity objective in Part 1C-1 is met if the noninferiority is demonstrated based on both coprimary endpoints.

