#### **6.4.3. Primary Analysis of Antibody-Mediated Immunogenicity Endpoints**

##### **Part 1C-1**

In the Part 1C-1 homologous booster phase, the noninferiority of the coprimary endpoints (Ab GM and SRR against the ancestral strain) in adolescents compared with those at Day 57 (28 days after Dose 2) in young adults (18-25 years of age) receiving mRNA-1273 in Study P301 will be assessed. The study is considered to meet the primary immunogenicity objective if the noninferiority of the immune response to mRNA-1273 as measured by both GM and seroresponse rate at BD-Day 29 is demonstrated in adolescents in this study at a 2-sided alpha of 0.05, compared with those at Day 57 (28 days after Dose 2) in young adults (18-25 years of age) in Study P301 receiving mRNA-1273.

The GM with 95% CI will be summarized using t-distribution of the log transferred values and then back transformed to the original scale. The GMR with 95% CI to compare post-booster GM at BD-Day 29 in adolescents in Study P203 with the primary series GM at Day 57 (28 days after Dose 2) in young adults (18-25 years of age) in Study P301 will be computed based on the t-distribution of mean difference in the log transferred values and then back transformed to the original scale. The noninferiority of immune response to mRNA-1273 as measured by GM will be considered demonstrated if the lower bound of the 95% CI of the GMR is  $> 0.667$  based on the noninferiority margin of 1.5, and GMR point estimate  $\geq 0.8$  (minimum threshold).

The number and percentage (rate) of participants achieving Ab seroresponse at BD-Day 29 will be summarized. The SRR difference with 95% CI (using Miettinen-Nurminen score method) to compare post-booster SRR at BD-Day 29 in adolescents in Study P203 with the primary series SRR at Day 57 (28 days after Dose 2) in young adults in Study P301 will be calculated. The noninferiority in seroresponse rate of adolescents in P203 compared to

adults of 18-25 years of age in P301 will be considered demonstrated if the lower bound of the 95% of the seroresponse rate difference is  $> -10\%$  based on the noninferiority margin of 10%.

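### The Part 1A GMR noninferiority limit is 0.667 in Section 4.2 but 0.67 in Section 6.4.3, and one Part 1C-1 seroresponse limit carries two inequality signs; both need a one-line correction

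*SAP*

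**What the plan says.** The file holds two SAPs: one for Part 1A, and one for Parts 1B, 1C, 2 and 3 (called the second SAP here).

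**Part 1A, geometric mean coprimary endpoint.** In Section 4.2 of the Part 1A SAP the first success criterion is: "The lower bound of the 95% CI of the geometric mean ratio (GMR) rules out 0.667 (lower bound > 0.667"), with a margin of 1.5. In Section 6.4.3, for the same endpoint, visit and comparison, the limit is "> 0.67$ based on the noninferiority margin of 1.5, and GMR point estimate" above 0.8. Both sections name the margin 1.5. The point-estimate criterion is the same in both; Section 4.2 words it as "The GMR point estimate > 0.8 (minimum threshold").

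**Other GMR noninferiority limits.** In the second SAP, Part 1C-1 (Sections 4.2.1.1, 4.2.1.2 and 6.4.3) and Part 3 (Sections 4.2.3 and 6.4.3) use 0.667 throughout.

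**Part 1C-1, seroresponse coprimary endpoint.** Section 4.2.1.1 of the second SAP says noninferiority is shown by "the lower bound of the 95% CI of the seroresponse rate difference" being "\geq -10\%$ (i.e. lower bound $> -10\%$ ) using the noninferiority margin of 10"%. Section 6.4.3 of the second SAP gives only "> -10\%$ based on the noninferiority margin of 10"%. The parallel key secondary hypothesis in Section 4.2.1.2 is also strict only.

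**The concern.** A confirmatory test should have one decision rule. Here the hypothesis section and the primary analysis section of the same SAP give different limits for the same coprimary test, so a lower bound of 0.668 is a success under one and a failure under the other.

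The documents do not say which section governs. Section 1 of the Part 1A SAP puts the SAP above the protocol where methods differ, but that does not settle a conflict inside the SAP. Section 7, which lists changes from the protocol, mentions only the added point-estimate criteria, so 0.67 is not declared as a deliberate change.

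The test also has standing beyond Part 1A. Under Section 4.4 of the second SAP, Part 1A is the first link of a fixed sequence that passes alpha to Part 1C-1 and then to Part 3. The seroresponse limit with two signs belongs to the second link.

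**Working it through.** **Inputs** (Part 1A SAP, Section 4.3): 289 per group, true GMR 1, margin 1.5, SD of log levels 1.5, 2-sided alpha 0.05, stated power 90%. Section 4.3 gives no log base. Natural log is assumed because it reproduces the stated power, whereas reading the SD on the log10 scale gives about 29%. Section 4.3.4 of the second SAP uses the same SD of 1.5 and says natural log.

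**1. Margin and limit.** 1/1.5 = 0.6667; 1/0.667 = 1.499; 1/0.67 = 1.4925. The 0.67 limit equals the reciprocal of 1.5 only after rounding to two decimals.

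**2. The plan's own power.** SE of log GMR = 1.5 × √(2/289) = 0.1248. Power = Φ(ln(1/limit)/SE − 1.96).

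| Limit | ln(1/limit) | Power, normal | Power, noncentral t | n per group for 90% |
|---|---|---|---|---|
| 1/1.5 | 0.4055 | 90.1% | 90.0% | 288 |
| 0.667 | 0.4050 | 90.1% | 90.0% | 289 |
| 0.67 | 0.4005 | 89.4% | 89.3% | 295 |

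The stated 289 per group and 90% are reproduced, and they belong to 0.667. Taken literally, 0.67 costs about 0.7 percentage points of power, or 295 − 289 = 6 more participants per group.

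**3. Observed GMR needed to pass.** exp(ln(limit) + 1.96 × SE) gives 0.852 for 0.667 and 0.856 for 0.67. An observed GMR between these values passes Section 4.2 and fails Section 6.4.3. It exceeds 0.8, so the point-estimate criterion does not settle the matter.

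**4. Probability of a split verdict.** This is the chance that the lower bound lies above 0.667 but not above 0.67, at true GMR g: Φ((ln g − ln 0.667)/SE − 1.96) − Φ((ln g − ln 0.67)/SE − 1.96).

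- g = 1.0: 0.6%
- g = 0.9: 1.3%
- g = 0.85: 1.4%
- Maximum over all g: 2Φ(ln(0.67/0.667)/(2 × SE)) − 1 = 1.4%

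**5. Dependence on the SD.** With a smaller SD the 0.8 criterion takes over. A lower bound of 0.67 goes with a point estimate of exactly 0.8 when SD = ln(0.8/0.67)/(1.96 × √(2/289)) = 0.1773/0.1631 ≈ 1.09. At or below that SD, every result in the gap fails under both sections and the conflict has no effect.

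**6. Seroresponse sign.** The limits ≥ −10% and > −10% separate only if the lower confidence bound equals −10% exactly. There is no other case to compute.

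**The case against.** The strongest reply is that 0.67 is a rounding slip whose meaning is plain. The margin of 1.5 stands beside it, every other GMR noninferiority limit in both SAPs is 0.667, and 0.67 is the stricter figure, so a literal reading cannot inflate the type I error. The double sign in Part 1C-1 glosses itself strictly in the same sentence, and the analysis section is strict. No pending decision turns on either: Sections 4.4 of the second SAP report the Part 1A coprimary tests as completed and significant on the 08 May 2021 snapshot, and Part 1C-1 as significant at an interim analysis with a 16 May 2022 cutoff.

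All of this stands, and it makes the point small. It does not remove it, because the text of a coprimary success criterion still gives two limits for one test.

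A reader might infer three stronger things that the documents do not support:

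- **That the 0.8 floor is also contradictory.** Part 1A requires the point estimate to exceed 0.8, and Part 1C-1 has "\geq 0.8$ (minimum threshold"). These are separate tests, and each wording is consistent within its own part (Sections 4.2, 6.4.3 and 7 for Part 1A; Sections 4.2.1.1, 4.2.1.2 and 6.4.3 for Part 1C-1). No single result can pass and fail because of it.
- **That the alpha chain or a reported conclusion is in doubt.** The SAPs give no observed confidence bounds, so no effect on either completed test can be shown.
- **That the sample size is wrong.** It reproduces with 0.667.

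**Conclusion.** The inconsistency is real, minor and confined to two places. Section 6.4.3 of the Part 1A SAP misstates the GMR limit set in Section 4.2. Section 4.2.1.1 of the second SAP prints two signs for one seroresponse limit.

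For the GMR limit, the chance that the choice of section changes the result is about 0.6% under the planning assumption and never above about 1.4%. This rests on 289 per group, SD 1.5 on the natural log scale and a normal approximation. For the seroresponse limit the chance is negligible. The evidence favours 0.667, since it matches the margin, the power statement and every other GMR noninferiority limit. The point is about having one clear rule on record, not about a doubtful result.

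**What to change.** 1. In Section 6.4.3 of the Part 1A SAP, change 0.67 to 0.667.
2. In the Part 1C-1 coprimary seroresponse hypothesis (second SAP, Section 4.2.1.1), change ≥ −10% to > −10%.
3. Record which GMR limit was applied in the completed Part 1A analysis (08 May 2021 snapshot), so that it is clear whether the choice affected the conclusion.

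Leave the Part 1C-1 point-estimate criterion of ≥ 0.8 as it is. It is consistent within its part, and rewriting it after the test has been reported would do more harm than good. Do not program an unrounded 1/1.5 either: it would be a third limit, slightly more lenient than both printed ones, introduced after the Part 1A result is known.

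The cost is two wording changes and one sentence of record, with no new data, analysis or sample-size work.

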#### **6.4.4. Secondary Analysis of Antibody-Mediated Immunogenicity Endpoints**

For each group, the following evaluations will be performed at each time point at which blood samples are collected for immunogenicity (unless otherwise specified).

- GM level of SARS-CoV-2-specific bAb levels with corresponding 95% CI will be provided at each time point. The 95% CIs will be calculated based on the t-distribution of the log-transformed values then back transformed to the original scale for presentation. GM level and corresponding 95% CI will be plotted at each timepoint. The following descriptive statistics will be also provided at each time point: the number of subjects (n), median, minimum and maximum.
- GM fold-rise of SARS-CoV-2-specific bAb levels with corresponding 95% CI will be provided at each post-baseline timepoint over pre-injection baseline at Day 1. The 95% CIs will be calculated based on the t-distribution of the log-transformed values then back transformed to the original scale for presentation. GM fold-rise and corresponding 95% CI will be plotted at each timepoint. The following descriptive statistics will be also provided at each time point: the number of subjects (n), median, minimum and maximum.

Proportion of subjects with fold-rise  $\geq 2$ , and fold-rise  $\geq 4$  of serum SARS-CoV-2 specific bAb levels from Visit Day 1 (baseline) at each post injection time points will be tabulated with 2-sided 95% Clopper-Pearson CIs.

- GMT of SARS-CoV-2-specific nAb titers with corresponding 95% CI will be provided at each time point using the same method mentioned above.
- GMFR of SARS-CoV-2-specific nAb titers with corresponding 95% CI will be provided at each post-baseline timepoint over pre-injection baseline at Day 1 using the same method mentioned above.

Proportion of subjects with fold-rise  $\geq 2$ , and fold-rise  $\geq 4$  of serum SARS-CoV-2-specific nAb titers from Visit Day 1 (baseline) at each post-injection time points will be provided using the same method mentioned above.

- Proportion of subjects with seroresponse due to vaccination will be tabulated with 2-sided 95% Clopper-Pearson CIs at each post-baseline timepoint.
- Per the study protocol, if the visit for the second dose (Day 29) is disrupted and cannot be completed at Day 29 (+7 days) as a result of the COVID-19 pandemic (self-quarantine or disruption of clinical site activities following business continuity plans and/or local government mandates for “stay at home” or “shelter in place”), the window may be extended to Day 29 + 21 days. More rigid visit window may be used in the Per-protocol Immunogenicity Subset as appropriate.

